## **8.7 Demographic, Medical History, Prior Medication and Other Baseline Characteristics**

Demographic characteristics, medical history, prior medication and other baseline data will be listed and summarized using descriptive statistics for continuation data and contingency tables for categorical data. Prior medication will be summarized by anatomical therapeutic chemical (ATC) terms.

## **8.8 Study Treatment**

The number of doses of BGB324 and pembrolizumab by cycle and over entire study period will be listed and summarized using descriptive statistics. The time on study drug until last treatment received will be listed and presented by descriptive statistics.

## 8.9 Concomitant Medication

Concomitant medication and significant non-drug therapies after the start of study treatment will be listed and summarized by ATC term in contingency tables.

## 8.10 Reasons for Discontinuation from Study Treatment

Reasons for discontinuation of study treatment(s) will be listed and summarized.

## 8.11 Primary Objectives

Objective response rate as defined by achieving complete response and/or partial response will be presented by percentage rates and 90% CIs. All response assessments will be listed.

Note that the Disease Assessment time point used for this analysis may vary, and need not be the first on treatment assessment. Where there is the possibility of an immune response leading to a false categorization of disease progression, results from later tumor imaging time points may be used for the ORR assessment following the  $k$ -stage design.

Objective response rate is defined as the percentage of patients with a CR or PR (out of the number evaluable), a 90% CI for the overall ORR will be calculated assuming an exact binomial distribution.

A patient who has discontinued both treatments, and subsequently responds having received a subsequent anti-cancer treatment may be excluded (at the statistical analysis) from the subset of responding patients (these patients are evaluable, and will be included in the denominator). Such patients will contribute to the time to progression and death Kaplan Meier plots.

All patients with a documented PR or CR are expected to have the result confirmed by repeat scan at least 4 weeks (28 days) later.

The ORR will further be explored as follows:

- By PD-L1 status (+ve/-ve), using a Chi square or Fishers Exact Test
- By Axl status (+ve/-ve), using a Chi square or Fishers Exact Test, and
- Summarized in a table of PD-L1 by Axl expression status to explore the ORR in each of the four quadrants (++, +-, -+, --). That is, patients will be allocated into one of the 4 groupings: where both Axl and PD-L1 are positive; where there is one positive and one negative and where there are both Axl and PD-L1 negative.

If the PD-L1 expression status is provided as a TPS or, in one of 3 categories usually <1%, 1-49% and  $\geq 50\%$ , the patient will be regarded as PD-L1 positive if their TPS is  $\geq 1\%$ .

A patient with Axl positive disease is defined as one with an expression level of 1+ or greater according to IHC staining intensity, although other cut offs may be considered.

For each patient, the best percentage change in tumor volume will be illustrated in a ‘waterfall’ plot.

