**Table 2: BGB324 and pembrolizumab dosing**

BGB324:	Loading Dose: Days 1, 2 & 3	Daily Dose: Day 4 onwards	Frequency	Route of administration
Dose level	400 mg	200 mg	Daily	Oral
Dose level -1	200 mg	100 mg	Daily	Oral
Pembrolizumab	Dose	Regimen	Frequency	Route of administration
	200 mg	Day 1 of each cycle	Every 3 weeks	IV

Dosing of both drugs will commence on Day 1. On days when both BGB324 and pembrolizumab are given, pembrolizumab will be given first and patients will be observed for 1 hour for infusion and other adverse events (AEs). BGB324 may then be administered.

BGB324 and pembrolizumab will be given until disease progression (note that in the absence of clinical deterioration, treatment can continue and clinical progression should be confirmed after 4 weeks) or until an unacceptable toxicity has occurred which necessitates treatment withdrawal ([Section 6.6](#)), or until 106 weeks (35 cycles), equivalent to 24 calendar months.

Patients who discontinue BGB324 treatment (for reasons other than disease progression) may be able to continue with (monotherapy) pembrolizumab until 106 weeks (that is, 35 completed cycles of pembrolizumab, equivalent to 24 calendar months).

Patients who discontinue pembrolizumab (for reasons other than disease progression) may be able to continue with BGB324 for up to 106 weeks (equivalent of 24 calendar months).

If a tumor imaging assessment is suggestive of progressive disease, but the patient has an absence of clinical deterioration, a confirmatory scan after 4 weeks (this may be an unscheduled scan) will be made in order to rule out a pseudo or false progression caused by an inflammatory immune response. In the absence of clinical deterioration, treatment with both BGB324 and pembrolizumab can continue until disease progression is confirmed.

As per RECIST 1.1, all patients who are considered to have a complete or partial response must have this response confirmed by a confirmatory scan at least 4 weeks later.

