### 5.3.10 Tumor imaging

Efficacy endpoints in this study, including ORR, DoR, PFS will all be based on tumor imaging evaluation by RECIST 1.1.

RECIST assessments will be performed at the times given in Schedule of Study Assessment Table 4 and Table 5 using contrast-enhanced CT (preferred method) or MRI assessments of chest, abdomen, and pelvis. X-ray scans can be used where appropriate. Bone scans and brain scans should be conducted in the 6 weeks prior to study entry. Subsequently, x-ray, bone scans and brain scans will be used as appropriate. Additional anatomy should be imaged based on signs and symptoms of individual patients at baseline and follow-up.

Baseline assessments should be performed no more than 28 days before start of study treatment (6 weeks for brain and bone scans), and ideally should be performed as close as possible to the start of study treatment. The Screening imaging assessments must confirm the patient has measurable disease per RECIST 1.1 (see [Section 3.1](#)).

For each patient, the same modality used at Screening must be used serially throughout the duration of study participation. All imaging procedures will be performed according to standard local imaging protocols to ensure consistency across study assessments.

All radiological and non-radiological (e.g. MRI) scans will be reviewed by the local site investigator; and if possible, stored electronically (de-identified with the patient's notes) at site.

A maximum of 5 target lesions (TLs) must be selected at baseline. All target lesions are measurable. Target lesions should be selected on the basis of their size (longest diameter for non-nodal lesions or short axis for nodal lesions), but in addition should be those that lend themselves to reproducible repeated measurements. All remaining lesions present at baseline are considered non-target, irrespective of whether they are measurable.

Disease assessments will be performed as per the schedule described in [Table 3](#), [Table 4](#) and [Table 5](#) – that is, every 9 weeks  $\pm 7$  days for the first 46 weeks relative to the date of first treatment administration and then every 12 weeks  $\pm 7$  days thereafter until confirmed objective disease progression as defined by RECIST 1.1 (irrespective of a delay to treatment, or the reason for stopping treatment or subsequent therapy).

Any other sites at which new disease is suspected should also be adequately imaged at a follow-up visit.

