## 6.10 Prohibited Concomitant Medications Whilst Receiving Pembrolizumab

Patients are prohibited from receiving the following therapies during the Screening and Treatment period (including retreatment for post-complete response relapse) of this trial:

- Antineoplastic systemic chemotherapy or biological therapy
- Immunotherapy not specified in this protocol
- Chemotherapy not specified in this protocol
- Investigational agents other than BGB324 and pembrolizumab
- Radiation therapy
  - Note: Radiation therapy to a symptomatic solitary lesion or to the brain may be considered on an exceptional case by case basis after consultation with Sponsor.

The patient must have clear measurable disease outside the radiated field. Administration of palliative radiation therapy will be considered clinical progression for the purposes of determining PFS. *Note: Treatment with pembrolizumab and BGB324 must have been discontinued at least one week prior to radiotherapy and should not be restarted within one week of completing radiotherapy.*

- Live vaccines within 30 days prior to the first dose of trial treatment and while participating in the trial. Examples of live vaccines include, but are not limited to, the following: measles, mumps, rubella, chicken pox, yellow fever, rabies, BCG, and typhoid (oral) vaccine. Seasonal influenza vaccines for injection are generally killed virus vaccines and are allowed. However, intranasal influenza vaccines (e.g. Flu - Mist®) are live attenuated vaccines, and are not allowed.
- Systemic glucocorticoids for any purpose other than to modulate symptoms from an event of clinical interest of suspected immunologic etiology. If a patient requires physiologic doses of corticosteroids, they must discontinue their BGB324.
  - Note: Inhaled steroids are allowed for management of asthma.

Patients who, in the assessment by the investigator, require the use of any of the aforementioned treatments for clinical management should be removed from the trial. Patients may receive other medications that the investigator deems to be medically necessary.

The Exclusion Criteria describes other medications that are prohibited in this trial.

There are no prohibited therapies during the Follow Up period once the patient has discontinued both treatments.

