#### 8.5 RECIST 1.1 and Disease Assessment

Efficacy endpoints in this study, including ORR, DoR, PFS will all be based on tumor imaging evaluation by RECIST 1.1.

RECIST assessments will be performed using contrast-enhanced CT/MRI assessments of chest, abdomen, and pelvis. Additionally, x-ray, bone scans and brain scans will be used as appropriate.

Additional anatomy should be imaged based on signs and symptoms of individual patients at baseline and follow-up. Baseline assessments should be performed no more than 28 days before start of study treatment (although bone scans and brain scans may be done within 6 weeks), and ideally should be performed as close as possible to the start of study treatment.

All radiological and non-radiological (eg, MRI) scans will be reviewed by the local site investigator; and if possible, stored electronically (de-identified with the patient's notes) at site.

A maximum of 5 target lesions must be selected at baseline. All target lesions are measurable. Target lesions should be selected on the basis of their size (longest diameter for non-nodal lesions or short axis for nodal lesions), but in addition should be those that lend themselves to reproducible repeated measurements.

All remaining lesions present at baseline are considered non-target, irrespective of whether they are measurable.

Disease assessments will be performed every 9 weeks  $\pm 7$  days for the first 46 weeks relative to the date of first treatment administration and then every 12 weeks  $\pm 7$  days thereafter until confirmed objective disease progression as defined by RECIST 1.1 (irrespective of the reason for stopping treatment or subsequent therapy).

Any other sites at which new disease is suspected should also be adequately imaged at follow/up.

If an unscheduled assessment was performed and the patient has not progressed, every attempt should be made to perform the subsequent assessments at their scheduled visits. This schedule is to be followed in order to minimize any unintentional bias caused by some patients being assessed at a different frequency than other patients.

**Table 20** provides the RECIST 1.1 evaluation and definitions of disease response (based on TLs).

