**Table 20: RECIST 1.1 evaluation and definitions of disease response**

Complete Response (CR)	Disappearance of all TLs since baseline. Any pathological lymph nodes selected as TLs must have a reduction in short axis to <10 mm.
Partial Response (PR)	At least a 30% decrease in the sum of the diameters of TLs, taking as reference the baseline sum of diameters
Stable Disease (SD)	Neither sufficient shrinkage to qualify for PR nor sufficient increase to qualify for PD
Progression of disease (PD)	At least a 20% increase in the sum of diameters of TLs and an absolute increase of at least 5 mm, taking as reference the smallest sum on study (this includes the baseline sum if that is the smallest on study).
Not Evaluable (NE)	Only relevant if any of the TLs were not assessed or not evaluable or had a lesion intervention at this visit. Note: if the sum of diameters meets the progressive disease criteria, progressive disease overrides not evaluable as a TL response

All patients who are considered to have had a complete or partial response must have this response confirmed by a confirmatory scan at least 4 weeks later.

Details of any new lesions will also be recorded with the date of assessment. The presence of one or more new lesions is assessed as progression, however, in the absence of clinical deterioration, treatment can continue. The suspected disease progression should be confirmed after 28 days.

A lesion identified at a follow up assessment in an anatomical location that was not scanned at baseline is considered a new lesion and will indicate disease progression.

The finding of a new lesion should be unequivocal: i.e., not attributable to differences in scanning technique, change in imaging modality, or findings thought to represent something other than tumor.

If a new lesion is equivocal, for example because of its small size, the treatment and tumor assessments should be continued until the new lesion has been confirmed. If repeat scans confirm there is a new lesion, then the progression date should be declared using the date of the initial scan.

Disease progression requires confirmation. The confirmatory scan should occur preferably at the next scheduled visit and no earlier than 4 weeks after the initial assessment of progression of disease (PD) in the absence of clinical deterioration.

The overall visit response will be derived using the algorithm shown in [Table 21](#).

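### Section 8.11 defines the tested response rate without requiring confirmation, although the synopsis and Section 8.5 require it, and leaves optional whether a response after another anti-cancer drug counts

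*Protocol*

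**What the plan says.** Section 8.11 gives the operative definition: "Objective response rate is defined as the percentage of patients with a CR or PR (out of the number evaluable". The word confirmed does not appear in it, nor in the objectives tables (Tables 1 and 9). The same section then says that patients with a "documented PR or CR are expected to have the result confirmed by repeat scan at least 4 weeks (28 days) later".

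Two other places are stricter. The synopsis text after Table 2 says "all patients who are considered to have a complete or partial response must have this response confirmed", with the scan at least 4 weeks later. Section 8.5, below Table 20, says that responders "must have this response confirmed by a confirmatory scan at least 4 weeks later". The synopsis paragraph on tumor imaging also says that a suspected response will be confirmed, at the next scheduled assessment or no earlier than 28 days later. Footnote 7 to the schedule tables says that it should be.

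Section 8.11 also covers the patient who stops both drugs, takes another anti-cancer treatment and then responds. Such a patient stays in the denominator but "may be excluded (at the statistical analysis) from the subset of responding patients".

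Section 8.1 sets the decision rule on the count of responses: stop for futility at 5 or fewer of 28, stop for activity at 11 or more of 28, otherwise reject at 17 or more of 56. It gives power 80.6% and one-sided type I error 0.048.

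**The concern.** The limits are exact integers, so single patients decide the outcome: 5 or 6, 10 or 11, 16 or 17. The trial is open-label and single-arm, and scans are read at the site. The event being counted therefore has to be fixed in the endpoint definition. Here one section requires confirmation, the section that defines the endpoint expects it, and none says how a CR or PR without a confirming scan is counted.

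The second wording leaves it open, once results are known, whether a response to a different drug is credited to the combination. Such a response can be recorded. Section 5.3.10 continues scans until confirmed progression "irrespective of a delay to treatment, or the reason for stopping treatment or subsequent therapy", Section 8.5 repeats "irrespective of the reason for stopping treatment or subsequent therapy", and Section 6.10 says "There are no prohibited therapies during the Follow Up period once the patient has discontinued both treatments".

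Both ambiguities can only raise the response rate relative to the strict reading. At the interim the DRC also weighs safety, duration of response and PFS (Section 8.2.2). The final test at 17 of 56 rests on the count alone.

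**Working it through.** **1. The plan's own figures.** Inputs from Section 8.1: 28 patients per stage, p0 = 0.20, p1 = 0.35, limits 5, 11 and 17. With X1 and X2 binomial(28, p):

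P(reject) = P(X1 ≥ 11) + Σ (x = 6 to 10) P(X1 = x) · P(X2 ≥ 17 − x)

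- p = 0.20: 0.0149 + 0.0334 = 0.0483 (stated 0.048).
- p = 0.35: 0.3840 + 0.4215 = 0.8055 (stated 80.6%, from simulation).
- Futility stop at p = 0.20: 0.5005 (stated 50.2%). Activity stop at p = 0.35: 0.384 (stated 38.4%).
- Expected size: 41.6 and 44.1 (stated 42-44).

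The design figures reproduce. They hold for whichever definition of response p0 and p1 refer to, if that definition is used throughout.

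**2. Illustration: unconfirmed responses counted.** The protocol gives no confirmation rate, so the shares are assumptions. If the true confirmed rate is 0.20 and a share u of counted responses do not confirm, the counted rate is 0.20/(1 − u).

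| u | counted rate | P(reject) |
|---|---|---|
| 0 | 0.2000 | 0.048 |
| 5% | 0.20/0.95 = 0.2105 | 0.072 |
| 10% | 0.20/0.90 = 0.2222 | 0.106 |

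**3. The reverse case.** If p1 = 0.35 was meant as any response and only confirmed responses count, the counted rate is 0.35(1 − u):

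- u = 5%: 0.3325, power 72.3%.
- u = 10%: 0.315, power 62.5%.

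**4. One patient who responds after a new therapy.** Fix one patient's outcome, with all others at p = 0.20:

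- Stage 1 patient: P(reject) is 0.040 if counted as a non-responder and 0.081 if counted as a responder.
- Stage 2 patient: 0.043 and 0.071.

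These are conditional on such a patient existing. They are not type I error rates.

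**5. Timing at the looks.** From Table 3, the scans within 24 weeks are at Weeks 10 and 19. Week 19 starts on day 18 × 7 + 1 = 127 (window 120-134). The earliest confirming scan for a Week 19 response is 28 days later, day 155 (148-162), before day 168 (24 weeks). The next scheduled scan, which the synopsis also allows for confirmation, is Week 28, day 27 × 7 + 1 = 190. That is 22 days after day 168. A response that follows the protocol can thus still be pending at the minimum cut.

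**6. Cost of scoring pending responses as failures.** Take p = 0.35, with a share of Stage 1 responses pending at the interim and recovered by the final look (shares assumed):

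| pending | futility stop | power |
|---|---|---|
| 0 | 3.9% | 80.6% |
| 10% | 8.4% | 78.0% |
| 20% | 16.2% | 72.9% |

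**The case against.** The strongest reply is that the intent is not in doubt. The synopsis and Section 8.5 require confirmation, Section 8.5 governs the RECIST-based endpoints, and even the softer wording in Section 8.11 points the same way. This stands. A reader might infer that the protocol counts unconfirmed responses, or that the stated alpha of 0.048 is wrong or inflated. The documents support neither: no passage says that an unconfirmed response counts, and the error rates are right for a single definition.

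A second reply is that Section 8.3 leaves data-handling rules, including missing data for the primary endpoint, to an SAP signed before database lock. That answers a complaint about missing detail. It does not answer two wordings that the protocol itself puts in its endpoint definition, one at odds with its other sections and one explicitly optional. Sign-off before lock is a real safeguard, but in an open-label trial it need not come before site-read responses are known.

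Third, the inflation figures rest on assumed non-confirmation shares and on every such response being counted against the stricter sections. The new-therapy route is also narrow, since the patient must stop both drugs without confirmed progression. Both points stand, and the figures should be read as illustration.

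Fourth, scoring every response unconfirmed at the cut as a failure would penalise valid late responses at the futility look. Step 6 of the working bears this out, so the fix must not do that.

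**Conclusion.** The point holds as a defect of definition in the primary endpoint. Section 8.11 is weaker on confirmation than the synopsis and Section 8.5, and it leaves to discretion whether a response after another anti-cancer drug is credited to the combination. The second is the clearer fault, because no other section settles it, but it will probably arise rarely.

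The size of any bias cannot be determined from the protocol. The values 0.072 and 0.106 assume a true confirmed rate of 0.20, 5% or 10% of counted responses unconfirmed, and all of those counted. Nor can it be determined whether the 18.5% cited in support of p0 was a confirmed rate, since that source is not at hand. The correction is worth making because it is cheap and the final decision turns on one integer count.

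**What to change.** 1. In Section 8.11, and in Tables 1 and 9, define a responder as a patient with a CR or PR confirmed by a scan at least 28 days later, in line with the synopsis and Section 8.5. Count a response that is never confirmed as a non-response. For a response still awaiting its confirming scan at the 24-week cut, obtain the scan already permitted from 28 days, or wait for it, before applying the 5/11 or 17 limits. Do not score it as a failure.
2. Replace the optional exclusion with a fixed rule: a response first documented after the start of a new anti-cancer therapy is counted as a non-response, and the patient stays in the denominator.
3. State that p0 = 0.20 and p1 = 0.35 refer to confirmed response. If p1 was meant as any response, restate the power (72.3% or 62.5% under the 5% or 10% assumption).

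Cost: wording changes, carried to the SAP, and no extra patients. Recruitment is already halted at the interim and the 24 weeks are worded as a minimum, so waiting costs at most a short delay, about three weeks from day 168 to the Week 28 scan (plus its 7-day window). Section 8.6 limits collection after the last-visit date to serious safety data, so that date should allow for any confirming scan still due.

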## 8.12 Secondary Objectives

### 8.12.1 Safety

#### 8.12.1.1 Adverse event

Adverse events will be coded as described in [Section 8.4](#). The number of AEs occurring at least once in a patient will be listed and summarized by contingency tables for:

- primary system organ class, preferred term;
- preferred term;
- NCI CTCAE grade;
- relationship to both study drugs;
- interruption of study drug;
- leading to discontinuation;
- Grade 3 and higher;
- SAEs;
- AEs leading to death;
- standard medical queries.

